6.2 Duplicate Data

For unplanned duplicate data within a protocol-specified visit, the last measured value will be used for the analysis. If it is not possible to identify the “last measured value” the average of the duplicate values will be used.

6.3 Handling of Missing Data

There will be no imputation of missing data for this study.

6.4 Multicenter Clinical Trials

Up to 30 centers in the United States.

6.5 Multiple Comparisons and Type I Error Rate Multiplicity adjustments

This is a proof of concept study and there is no need for adjustment of Type I error rate.

6.6 Covariates and Prognostic Factors

There are no pre-planned covariates analyses of the data from this study.

6.7 Stratification Factors

There are no stratification factors for this study.

6.8 Subgroups and Exploratory Analysis

There are no subgroups and exploratory analysis for this study.

6.9 Standard Calculations

6.9.1 Age

Age will be calculated as the number of completed years between the date of informed consent and the subject's birth date.

Age (years) = integer off[(date of informed consent – date of birth)/ 365.25+ 0.5]

6.9.2 Weight

For summary purposes weight will be expressed in kilograms. Entries made in pounds will be converted to kilograms using the formula noted below.

$$\text{Weight (kg)} = \text{Weight (lb)} / 2.2046$$

6.9.3 Change from baseline

Change from baseline will be calculated for each post baseline visit as follows:

$$\text{Change From Baseline} = \text{Post baseline result at time t} - \text{Baseline result}$$

7. STATISTICAL METHODS

All collected study data will be presented in subject data listings. Statistical analyses will be performed using SAS® for Windows, version 9.4 or later.

7.1 Summarizing and Tabulating the Collected Data

All data collected will be summarized according to the variable type:

- Continuous data summaries will include number of observations, mean, standard deviation, median, and minimum and maximum values.
- Categorical data summaries will include frequency counts and percentages.

7.1.1 Subject Disposition and Withdrawals

- There will be a detailed accounting of all subjects that signed the informed consent to participate in this trial. The following will be summarized: The number of subjects who are screenedThe number of subjects who received treatment
- The number of subjects who completed the study
- The number of subjects who discontinued during the study
- The reason for all post treatment study discontinuation

In addition, there will also be a listing of all discontinued subjects, which will provide the specific reason for discontinuation.

7.1.2 Protocol Deviations

The deviations occurring during the clinical trial will be summarized descriptively according to the following categories:

- Informed Consent deviation
- Inclusion/Exclusion criteria deviation
- Developed withdrawal criteria deviation
- Procedure performed out of window
- Received an excluded concomitant medication
- Missed procedure
- All other deviations

Additionally a by-subject listing of all deviations will also be prepared.

7.1.3 Demographics and Baseline Characteristics

Demographic and baseline characteristics (i.e., Age, Gender, Time since HIV diagnosis, Viral load at T1, etc.) will be summarized using appropriate descriptive statistics.

Medical history of the subjects will also be provided as a by-subject listing.

7.1.4 Prior and Concomitant Medications

Prior and concomitant medications will be summarized for the Safety population. All prior and concomitant medications recorded in the eCRFs will be coded to generic term and all matching Anatomic Therapeutic Classification (ATC) codes using WHO Drug Summaries will be prepared using the coded terms. All prior and concomitant medications recorded in the eCRFs will also be listed.

7.1.5 Antiretroviral Therapy

Antiretroviral Therapy is not captured in this study but data captured in the PRO140_CD02 and PR140_CD02 Open Label used to summarize the data for to PRO140_CD02_Extension.

Anti-retroviral therapy will be summarized for the Safety Population. All such medications recorded in the eCRFs will be coded to generic term and all matching Anatomic Therapeutic Classification (ATC) codes using WHO Drug Summaries will be prepared using the coded terms. All anti-retroviral therapy recorded in the eCRFs will also be listed.

7.1.6 Optimized Background Therapy (OBT)

Optimized background therapy will be summarized for the Safety Population. All such medications recorded in the eCRFs will be coded to generic term and all matching Anatomic Therapeutic

Classification (ATC) codes using WHO Drug. Summaries will be prepared using the coded terms. All optimized background therapy recorded in the eCRFs will also be listed.

7.1.7 Treatment Administration

PRO 140 will be administered as a 350mg subcutaneous injection weekly during treatment extension phase in addition to OBT.

A total of 700 mg (175 mg/mL) is delivered as two 2 mL injections administered subcutaneously on opposite sides of the abdomen.

Subjects who were enrolled under a Protocol version 4.0 and are still receiving the 350 mg dose, have the option of increasing their dose to 700mg for the remainder of the Treatment Extension Phase.

Note: IP must be administered by a qualified medical professional (MD, DO, PA, LPN, LVN, NP, RN or CMA if permitted by state law) or self-administered by subjects.

All treatment PRO-140 administration data will be listed. In addition, the number and percentage of the subjects who received PRO-140 injection will be presented for the safety population for each week during the treatment period.

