6.4 INVESTIGATIONAL PRODUCT ADMINISTRATION

Guidelines for dose preparation can be found in the PRO140_CD02 or CD02_OpenLabel Pharmacy Manual.

PRO 140 will be provided to the administering personnel in single-use syringes prepared from vials of study drug stored at 2-8°C at the site pharmacy prior to use. Each of two syringes is filled to deliver 2.0 mL of study drug.

Equivalent volumes of study drug will be administered subcutaneously on opposite sides of the abdomen.

A 25-gauge needle should be used to remove IP from vial and for administration to subjects.

IP should be administered slowly over 15 seconds per mL. IP should not be kept in syringe for longer than 60 minutes.

Following each SC delivery of drug, careful examination will be made to assess the appearance of any study drug Injection Site Reactions (ISRs) as described in [Section 16.3](#).

All doses of study drug will be prepared by either the credentialed pharmacist or qualified medical professional and will be administered as SC injection by a qualified medical professional (MD, DO, PA, LPN, LVN, NP, RN, or CMA if permitted by state law) or self-administered by subjects depending on the study visit week.

Note: It is preferred that the same injection site be used throughout the study. At the same time, it is not recommended to inject the study drug into areas where skin shows signs of a previous injection site reaction. It is advised to change the injection site if any previous injection site reaction remains unresolved. Alternatively, the 700 mg dose may be delivered as four 1mL doses (two SC injections on opposite sides of abdomen) for those that experience discomfort with the 2mL injections (i.e. subjects with low body fat percentages).

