7.13 INJECTION SITE REACTION ASSESSMENT

At each treatment visit that occurs at the clinical site, an injection site reaction assessment will be made for the current and previous injection sites. Injection site reaction assessments are recorded

by the Investigator starting after the first injection is given. Refer to [sections 9.1.8](#) and [16.3](#) for more details.

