2.3 Study Treatment

2.3.1 Treatment Group

This is a single arm study. All eligible subjects will receive PRO 140 SC injection and Optimized Background Therapy . PRO 140 as a 350mg dose (per protocol prior to v4.0) or 700mg (per protocol after v4.0) subcutaneous injection weekly until one of the following occurs:

- Virologic failure
- Consent withdrawn
- PRO 140 is approved
- CytoDyn decides to discontinue its development

NOTE: Subjects enrolled prior to Protocol v4.0 may still be receiving the original 350mg dose and have the option of increasing their dose to 700mg.

Study Drug	Dosage Form	IP concentration	Dosing Frequency and Amount	Route of Administration
PRO 140 350mg	Parenteral solution	175 mg/mL	2 injections of PRO 140 (2 X 1 mL/inj.) for 48 weeks	SC injection
			for 48 weeks	

PRO 140 700mg		Parenteral solution	175 mg/mL	2 injections of PRO 140 (2 X 2 mL/inj.) for 48 weeks	SC injection
---------------	--	---------------------	-----------	--	--------------

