2.4 Study Outcome Measures

- Mean change in viral load (HIV-1 RNA levels) at the conclusion of treatment period
- Mean change in CD4 cell count at the conclusion of treatment period
- Emergence of Dual/Mixed (D/M)- and CXCR4-tropic virus in patients who had exclusive CCR5-tropic virus at study entry.
- Tolerability of repeated subcutaneous administration of PRO 140 as assessed by investigator-evaluation of injection site reactions
- Frequency of treatment-related adverse events resulting in study drug discontinuation
- Frequency of Grade 3 or 4 adverse events as defined by the DAIDS Adverse Event scale

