7.2.4.2 Tolerability Assessment

7.2.4.3 Injection Site Reaction

At each visit during the Treatment Extension Phase, an injection site reaction assessment will be made for the current and previous injection sites. Injection site reaction assessments are recorded by the Investigator starting after the first injection is given. All data from the injection site reaction assessments of the repeated subcutaneous administration of PRO 140 will be presented and descriptively summarized.

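### The weekly injection count and the injection-site-reaction summary name no dose split, so each can combine 350 mg with 700 mg and describe neither dose

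*SAP*

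**What the plan says.** SAP 2.4 names as an outcome "Tolerability of repeated subcutaneous administration of PRO 140 as assessed by investigator-evaluation of injection site reactions".

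SAP 2.3.1 calls the study single arm but tabulates two regimens at 175 mg/mL. The 350 mg row reads "2 injections of PRO 140 (2 X 1 mL/inj" and the 700 mg row gives two injections of 2 mL. Under Protocol 3, subjects enrolled under versions 1.0 to 3.0 may stay on 350 mg or move to 700 mg. Under Protocol 1.5, new enrolees from version 4.0 receive 700 mg. Protocol 6.4 and SAP 2.2 also allow 700 mg as four 1 mL injections, "for those that experience discomfort with the 2mL injections (i.e. subjects with low body fat percentages".

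The two planned summaries are:

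- Exposure (SAP 7.1.7): "the number and percentage of the subjects who received PRO-140 injection will be presented for the safety population for each week". Administration data are also listed.
- Local tolerability (SAP 7.2.4.3): "All data from the injection site reaction assessments of the repeated subcutaneous administration of PRO 140 will be presented and descriptively summarized".

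SAP 7.2 runs the outcome measures on the Safety population, which SAP 5.1 defines as anyone given at least one dose of PRO 140. SAP 6.8 states: "There are no subgroups and exploratory analysis for this study". SAP 7.1 adds in general terms that "All data collected will be summarized according to the variable type", and SAP 9.2 lists table headings only.

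**The concern.** ISRs are a local effect, and the usual 700 mg regimen puts twice the volume into each site. The four-injection option shows that the sponsor foresaw discomfort at 2 mL in at least some subjects. Yet no section asks for the tolerability outcome to be shown by dose, and the exposure table would not reveal how many subjects were on each dose in a given week.

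What is at stake is whether one named outcome can be interpreted. A reader wants to know how the current dose is tolerated locally. A single figure over both doses is a weighted average, with weights set by how many subjects stayed on 350 mg and for how long. The point is confined to the ISR and exposure summaries. It makes no claim about viral load or CD4 count.

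**Working it through.** **1. The regimens (SAP 2.3.1; Protocol 6.4).** Dose = injections x mL per injection x 175 mg/mL.

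- 2 x 1 x 175 = 350 mg
- 2 x 2 x 175 = 700 mg
- 4 x 1 x 175 = 700 mg

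The stated doses reproduce. Volume per injection is 2 mL against 1 mL, a ratio of 2, except under the four-injection option. Neither the number of injections nor the volume of one injection identifies the dose: two injections can be 350 or 700 mg, and so can a 1 mL injection. Dose has to come from the recorded dose or from total volume.

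**2. Is a split required anywhere?**

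| Place | Content | Dose split? |
|---|---|---|
| SAP 2.3.1 | Two regimens tabulated, study called single arm | Regimens named, no analysis stated |
| SAP 5.1, 7.2 | Safety population, any dose | No |
| SAP 6.8 | No subgroups | No |
| SAP 7.1.7 | Weekly number and percentage injected | No |
| SAP 7.2.4.3 | Descriptive ISR summary | No |
| SAP 9.2 | Table headings | Silent |
| Protocol 8.7.5.1 | Adverse event tables by treatment group | Possible, but for treatment-emergent adverse events only |
| SAP 7.2.4.1 | Adverse event tables overall, by severity, by relationship | No; treatment group not carried over |

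**3. Size.** Let w be the share of assessed subjects or injections at 350 mg, and p350 and p700 the ISR rates.

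- Pooled rate = w x p350 + (1 - w) x p700
- 700 mg rate minus pooled rate = w x (p700 - p350)

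The documents give none of w, p350 or p700, so no estimate is possible. Purely as an illustration, with assumed values:

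| p350 | p700 | w | Pooled | p700 minus pooled |
|---|---|---|---|---|
| 10% | 10% | 50% | 10% | 0 points |
| 10% | 30% | 50% | 0.5 x 10 + 0.5 x 30 = 20% | 10 points |
| 10% | 30% | 70% | 0.7 x 10 + 0.3 x 30 = 16% | 14 points |
| 10% | 30% | 90% | 0.9 x 10 + 0.1 x 30 = 12% | 18 points |
| 30% | 10% | 50% | 0.5 x 30 + 0.5 x 10 = 20% | -10 points |

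The gap vanishes when the rates are equal or nobody is on 350 mg, and its sign follows whichever rate is higher.

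**4. Denominator.** Protocol 7.13 limits the assessment to clinic visits: "At each treatment visit that occurs at the clinical site, an injection site reaction assessment will be made for the current and previous injection sites". Subjects may also inject themselves, so injections given exceed injections assessed. A rate per injection should use assessed injections. Because long-stay subjects would dominate it, a count of subjects is needed beside it.

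**The case against.** The strongest reply is that the SAP is silent on dose; it does not order pooling. SAP 7.2.4.3 says the ISR data will be presented and summarised, and a table shell could add dose columns. Protocol 9.1.8 treats ISRs as adverse events of special interest, Protocol 8.7.5.1 tabulates adverse events by treatment group, and the SAP section headed Treatment Group lists both doses. A programmer might put these together and produce dose columns in the adverse event tables. Also, the primary objective is continued access, enrolment is capped at 50, no inference is planned for safety data, and listings would let a reader rebuild each subject's dose history.

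Much of this stands. A reader should not infer that the SAP instructs pooling, nor that the information is lost. But the treatment-group wording covers adverse event tables only, both documents call the study single arm, and SAP 7.2.4.1 drops the phrase. With 6.8 ruling out subgroups, the plain reading is one undivided ISR summary.

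Two other inferences are tempting and go too far.

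- **That most subjects are on 350 mg.** Protocol Table 1-1 shows 52 subjects in CD02 at 350 mg, and 25 planned with 2 analysed in CD02 Open Label at 700 mg. If the extension filled to 50, at least 50 - 25 = 25 (50%) would come from CD02, or 50 - 2 = 48 (96%) if only the 2 rolled over. But 50 is a ceiling, the Open Label study was still running, entry requires completing 24 weeks with suppression at T23, and subjects who began on 350 mg may switch. Feeder study does not give the dose received.
- **That the protocol shows ISRs rise with volume.** The four-injection option is a comfort provision, with low body fat given as its case. It makes a volume effect plausible and gives no rate.

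**Conclusion.** The point holds as a gap in the specification that is worth closing. As written, the weekly count and the ISR summary can combine 350 mg with 700 mg, and the named tolerability outcome would then describe neither dose. The conclusion rests on the text of SAP 5.1, 6.8, 7.1.7, 7.2 and 7.2.4.3, and on both doses being permitted in the study.

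No size can be put on the distortion. It depends on the dose mix and on ISR rates by dose, neither of which is given, and it is zero if the rates are equal. The illustrative gaps above only reflect the values assumed. No planned test, error rate or primary objective is affected.

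**What to change.** - **SAP 7.2.4.3.** Present ISR frequency and worst grade by dose received at the time of the injection (350 mg, 700 mg), plus a total. Give both subjects and clinic-assessed injections as denominators. Show any 700 mg given as four 1 mL injections as its own row. A pooled 1 mL column would mix 350 mg subjects with 700 mg subjects moved to smaller injections because of discomfort.
- **Attribution.** Assign a reaction to the dose of the injection that caused it. Protocol 6.4 prefers one site throughout, so current and previous sites may coincide. Where they cannot be told apart, assign the reaction to the most recent injection at that site.
- **SAP 7.1.7.** Show the weekly count by dose received. Derive dose from the recorded dose or total volume x 175 mg/mL, not from injection count or enrolment version.
- **SAP 6.8.** State that this descriptive split is planned, with no formal comparison, because dose is self-selected among earlier enrolees and tied to enrolment version.
- **Editorial, separate from the above.** The sentence in SAP 7.1.7 on subjects still receiving 350 mg places their enrolment under version 4.0. It should say prior to version 4.0, as the note in SAP 2.3.1 does.

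The cost is extra columns and one row in two descriptive tables and a sentence in 6.8. Cells will be small at up to 50 subjects. Dose or volume per injection must be in the administration data, and the documents do not show the eCRF fields, so this should be checked before the shells are fixed.

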7.2 Analysis of Study Outcome Measures

The analysis of study outcome measure will be conducted on the safety population.

7.2.1 Mean change in viral load (HIV-1 RNA levels)

The raw and change from baseline in HIV-1 RNA levels (log10 copies/mL) will be summarized atleast once every four week during the treatment extension phase. For change from baseline summaries, subjects with an undefined change from baseline, because of missing data, will be excluded.

7.2.2 Mean change in CD4 cell count

The raw and change from baseline in CD4 cell count will be summarized for each week during the treatment phase. The summary tables will include the number of observations, mean, standard deviation, median, and minimum and maximum values. For change from baseline summaries, subjects with an undefined change from baseline, because of missing data, will be excluded.

7.2.3 Emergence of Dual/Mixed (D/M) - and CXCR4-tropic virus

The data for this outcome measure will be provided by external vendor Monogram Biosciences. All patients have exclusive CCR5-tropic (i.e., R5 or X4) virus at study entry. The proportion of subjects with any tropism result of dual/mixed will be summarized.

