7.2.9.4 HIV-1 Trofile® DNA/RNA Assay and Drug Resistance, Genotypic and Phenotypic data

Data for HIV-1 trofile® DNA/RNA assay as well us Drug Resistance, Genotypic and Phenotypic data will be provided by external vendor Monogram Biosciences. All data will be presented as by-subject listings.

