Hepatic function indicators: total and direct bilirubin, alkaline phosphatase, aspartate aminotransferase (AST), alanine aminotransferase (ALT), total protein, Lactate dehydrogenase (LDH)
Renal function indicators: BUN, creatinine
Electrolytes: sodium, potassium, chloride, calcium and bicarbonate
Other: glucose (random), cholesterol (total)
- [8] Prothrombin time (PT) and International Normalized Ratio (INR)
- [9] Urine samples will be tested for color, appearance, specific gravity, pH, protein, glucose, occult blood, ketones, leukocyte esterase, nitrite, bilirubin, urobilinogen, and microscopic examination of urine sediment.
- [10] ONLY performed on women of childbearing potential. Subject will not be allowed to participate if the result is positive.
- [11] Plasma HIV-1 RNA and TruCount T Assay will be performed once every 4 weeks when subject comes to clinic. TruCount T Assay includes: CD3 %, CD4 %, CD8 %, Absolute Lymphocytes, CD3 cell count, CD4 cell count, and CD8 cell count
- [12] Injection Site Reaction will be assessed by the Investigator whenever IP administered at the clinic.
- [13] Monogram Biosciences Trofile® RNA and PhenoSense® Entry Assays [AMD3100 (CXCR4 inhibitor drug), Maraviroc and PRO 140 (CCR5 inhibitor drugs)]
- [14] Monogram Biosciences PhenoSense® GT Assay
- [15] Every 12 weeks during Treatment Extension.

TABLE 8-2: SCHEDULE OF ASSESSMENTS – FOLLOW-UP (FU) PHASE

(a) Subjects who do NOT experience virologic failure

Procedure/Assessments	Follow-Up Visit -1	Follow-Up Visit -2
	NVF-EFU1	NVF-EFU2
Window Period	2 weeks (±3 days) after EOT2 visit	4 weeks (±3 days) after EOT2 visit
Physical Examination	X ^[1]	X ^[1]
Vital Signs	X	X
Plasma HIV-1 RNA level	X	X
TruCount T assay	X	X
Adverse Events	X	X
Concomitant Medications	X	X

[1] Symptom-directed physical examination

(b) Subjects who experience virologic failure

Procedure/Assessments	Follow-Up Visit -1	Follow-Up Visit -2	Follow-Up Visit -3 ^[1]
	VF-EFU1	VF-EFU2	VF-EFU3
Window Period	4 weeks (±7 days) after VF visit	8 weeks (±7 days) after VF	12 weeks (±7 days) after VF
Physical Examination	X ^[2]	X ^[2]	X ^[2]
Vital Signs	X	X	X
Plasma HIV-1 RNA level	X	X	X
TruCount T assay	X	X	X
Adverse Events	X	X	X
Concomitant Medications	X	X	X

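### SAP 7.2.3 does not fully analyse its endpoint: the one proportion it specifies counts dual/mixed results and leaves out CXCR4-only results

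*SAP*

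**What the plan says.** SAP 2.4 lists the outcome as "Emergence of Dual/Mixed (D/M)- and CXCR4-tropic virus in patients who had exclusive CCR5-tropic virus at study entry". Protocol 8.2 and 8.7.4 list the same measure with the same two components, and the heading of SAP 7.2.3 repeats both: "Emergence of Dual/Mixed (D/M) - and CXCR4-tropic virus".

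Under that heading the SAP describes entry status as follows: "All patients have exclusive CCR5-tropic (i.e., R5 or X4) virus at study entry". It then gives its only analysis sentence: "The proportion of subjects with any tropism result of dual/mixed will be summarized".

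Four other places bear on the point:

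- **Population.** SAP 7.2 states: "The analysis of study outcome measure will be conducted on the safety population". SAP 5.1 defines that population as everyone who received at least one dose.
- **General summaries.** SAP 7.1 has all collected data summarised by variable type and adds: "Categorical data summaries will include frequency counts and percentages". Protocol 8.7.4 attaches a similar rule to its list of measures, which includes this one.
- **Listings.** SAP 7.2.9.4 says of the Trofile and resistance data: "All data will be presented as by-subject listings".
- **Timing.** Protocol 7.11.7 and the schedules in both documents place the Trofile assay at the virologic failure visit only.

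**The concern.** PRO 140 blocks CCR5, so a shift to CXCR4 use is one of the main things to look for when suppression is lost. Protocol 1.5 itself relies on the absence of altered tropism when it argues about the likely cause of viral rebound. A summary that cannot register one of the two named kinds of shift is weaker evidence on that question than the endpoint promises. In the extreme case the endpoint figure would be zero although an event of the defined kind had been observed.

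Two smaller matters sit beside it. The gloss on entry status puts the event to be detected inside the definition of being free of it. And because only subjects with virologic failure are scheduled for the assay, a proportion over all treated subjects, shown without the number tested, could be read as though every subject had been tested.

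**Working it through.** The plan states no figure to reproduce. The check compares texts and adds one line of arithmetic.

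**1. Endpoint against numerator.**

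| Place | Dual/mixed | CXCR4 |
|---|---|---|
| Protocol 8.2 and 8.7.4 | named | named |
| SAP 2.4 | named | named |
| SAP 7.2.3, heading | named | named |
| SAP 7.2.3, proportion to be summarised | counted | not mentioned |

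The rest of the SAP was checked for another CXCR4 summary. SAP 7.1 is a general rule that names no event. SAP 7.2.9.4 gives listings. Appendix 2 contains only category titles. None of them changes the numerator in 7.2.3.

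**2. Size.** Let d be the number of subjects with a dual/mixed result, x the number with a CXCR4-only result, and N the denominator.

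- As specified: d/N
- As the endpoint is defined: (d + x)/N
- Difference: x/N

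N = 50 is the planned maximum (Protocol Synopsis). The values of d and x, and N = 25, are assumptions.

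| N | d | x | As specified | As defined | Difference |
|---|---|---|---|---|---|
| 50 | 0 | 1 | 0/50 = 0% | 1/50 = 2% | 2 points |
| 50 | 1 | 1 | 1/50 = 2% | 2/50 = 4% | 2 points |
| 50 | 2 | 1 | 2/50 = 4% | 3/50 = 6% | 2 points |
| 25 | 0 | 1 | 0/25 = 0% | 1/25 = 4% | 4 points |
| any | any | 0 | d/N | d/N | none |

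The documents give no expected x. The earlier studies described in the protocol mention five subjects with a result other than R5: two in study 1302 (section 1.4.2.4) and three in CD01 (section 1.4.2.7). All five were dual/mixed, so x = 0 is quite possible.

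**3. Gloss.** Exclusive use of one co-receptor cannot mean either of two tropisms. X4 is in neither abbreviation list; it is read here in its usual sense of CXCR4-tropic. The endpoint wording sets CXCR4 against CCR5, and the SAP's Appendix 1, footnote 13, also keeps the two apart: "AMD3100 (CXCR4 inhibitor drug), Maraviroc and PRO 140 (CCR5 inhibitor drugs". No planned filter or derivation uses the gloss, so correcting it changes no number.

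**4. Denominator.** Let m be the number of subjects with a tropism result. Since the assay is scheduled only at virologic failure, m will be smaller than N unless every subject fails or is tested off schedule. SAP 7.2 points to N, SAP 6.3 rules out imputation of missing data, and no sentence says how the N − m untested subjects are treated. The figures (d + x)/N and (d + x)/m answer different questions, and the SAP asks for neither m nor the second figure.

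**5. Timing.** The analysis sentence sets no start date for the results it counts, although emergence implies a change after entry. The extension schedules no tropism test before virologic failure, so this matters only if results from the parent study are merged in. SAP 6.1 does take baseline from the parent study, so the entry result needs to be identified.

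**The case against.** The strongest reply is that a CXCR4 result would not be lost. Protocol 8.7.4 names this measure and requires counts and percentages for categorical data, SAP 7.1 does the same for all collected data, and SAP 7.2.9.4 lists every tropism result. A programmer could well produce a row for each tropism category. This stands as far as it goes: the result could be visible somewhere in the report. But the section written for this endpoint states a specific numerator, and the general rules do not add CXCR4 to it.

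It is also fair to say that the event may never occur, that every non-R5 result described so far was dual/mixed, and that the study is single-arm and descriptive. All of that limits the consequence. It does not make the stated rule match the endpoint.

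Two stronger readings are tempting and should be resisted:

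- A reader might infer that SAP 7.2.3 fails to analyse its endpoint altogether. It does not: the dual/mixed component is summarised.
- A reader might infer that untested subjects are counted as showing no emergence. No document says so. SAP 7.2 sets the population, SAP 6.3 bars imputation, and there is no rule for subjects without a result. What can be said is that their handling is not stated.

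**Conclusion.** The point holds for the numerator. As written, the endpoint proportion omits one of the two event types that define the endpoint, by 1/N for each CXCR4-only subject: 2 percentage points at N = 50, 4 points at an assumed N = 25, and nothing if no such result occurs. This rests on reading the analysis sentence literally and on treating dual/mixed and CXCR4 as separate result categories, as the endpoint wording does.

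The gloss is a plain wording error with no numerical effect. The denominator is an omission: the handling of untested subjects is unspecified. No error rate, sample size or decision rule depends on any of this. It should still be corrected, because the rule would give the wrong endpoint figure if the event occurred and the correction is cheap.

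**What to change.** Amend SAP 7.2.3 before database lock:

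- Define emergence as any tropism result of dual/mixed or CXCR4 (X4) obtained after the first extension treatment (TE1), in subjects with exclusive R5 virus at study entry.
- State which parent-study tropism result defines entry status.
- Report dual/mixed, CXCR4, and the two combined.
- Change the gloss on exclusive CCR5 tropism to R5 only.
- Beside the Safety population proportion, show the number of subjects with a tropism result and the proportion among them.

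The cost is a few sentences and a few table rows. No new assay or data collection is needed, since SAP 7.2.3 and 7.2.9.4 already have the tropism data supplied by the vendor.
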